### **4.4.2 Data Collection and Follow-up for Withdrawn Subjects**

Subjects taken off study due to treatment related toxicity will be followed until resolution or stabilization. All subjects will be followed for survival status regardless of the cause of death.

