## **4.4 Early Withdrawal of Subjects**

### **4.4.1 When and How to Withdraw Subjects**

Subjects who do not complete the study protocol will be considered to have prematurely discontinued the study. The reasons for premature discontinuation (for example, voluntary withdrawal, toxicity, death) must be recorded on the case report form (CRF). Final study evaluations will be completed at the time of discontinuation if it is possible. Reasons for withdrawal include, but are not limited to the following:

1. Inter-current illness that would, in the judgment of the investigator, affect assessments of clinical status to a significant degree or require discontinuation of study;
2. Unacceptable toxicity: Subjects will be followed until resolution or stabilization;
3. Disease progression;
4. Subject withdraws consent;
5. Treatment delay greater than four weeks for any toxicity;
6. Subjects who do not have satisfactory compliance with study procedures;
7. Major protocol violations, including, but not limited to:
  - a. failure to meet major inclusion/exclusion criteria;
  - b. failure to complete full evaluations as required by protocol;
  - c. use of concomitant therapies.

If any subject in a cohort discontinues early for reasons other than toxicity from immunotherapy, consideration will be given for replacement.

If a subject discontinues Study Treatments before completion of long term follow up for 6 months post the last dose of immunotherapy, all assessments for the end of Study Treatment visit and/or end of study visit should be performed.

Subjects who have disease progression confirmed and/or start new anti-cancer therapy will be discontinued from the study. In both Cohorts, subjects who progress in their disease, once confirmed, will be required to come for the end of the study visit. All subjects will be followed for survival status regardless of the cause of death.

In the case of a fatal outcome, all relevant information (including cause of death, autopsy report, ER/hospital record, concomitant medication, and relationship to Study Treatment or underlying disease) will be collected.

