### 6.6.1 Management of anxiety and pain due to EP procedure

Subjects will be offered topical anesthetic (e.g. EMLA), to limit significant discomfort from the vaccination/EP procedure. If EMLA (lidocaine 2.5% and prilocaine 2.5%) is used, an approximately 1.5 cm diameter amount will be applied with occlusion to the site of injection ~30 minutes prior to vaccination/EP. Subjects will be offered an analgesic (e.g. ibuprofen, ketorolac) after vaccination/EP. In case subjects are anxious for the procedure, they will be offered a mild sedative (e.g. 0.5-1.0 mg lorazepam), or equivalent, as a mild sedative for anxiety related to the vaccination/EP procedure. Mild sedatives may be administered approximately 1 hour prior to EP. Subjects who receive a mild sedative should not operate a motor vehicle for 3-4 hours after receiving medication and should have arranged transportation to depart the study site. Subjects who are allergic to or have contraindications to EMLA, ibuprofen, ketorolac or a mild sedative will be offered a suitable alternative.

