### 7.2 Statistical Methods

The primary analysis will estimate safety parameters. The incidence of SAEs and the incidence of injection site reactions will be estimated along with exact Clopper Pearson 95% confidence intervals. Toxicity experience will also be recorded and summarized.

In secondary analyses, immune response parameters will be estimated. For continuous outcomes, the mean and 95% confidence interval will be calculated using a t-distribution approach, and for binary outcomes, the proportion and exact Clopper Pearson 95% confidence interval will be calculated.

In exploratory analyses, we will also estimate the distributions of progression-free survival (PFS) and overall survival (OS) will be estimated, and any observed anti-tumor responses will be summarized. PFS and OS will be measured from the time of instillation of the initial dose of immunotherapy. Both The variables will be potentially censored by the end of the subject's observation. These distributions will be summarized using Kaplan-Meier survival curves and estimated median time to event of each type. Anti-tumor response category frequencies will be calculated.

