### 7.3 Subject Population(s) for Analysis

Any subject who receives at least one dose of treatment will be included in the safety analyses. For immunogenicity and survival/anti-tumor analyses, the main analyses will utilize subjects who received their assigned number of doses.

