#### **8.1.8 Post-study Reporting Requirements**

All AEs and SAEs including deaths, regardless of cause or relationship, must be reported for subjects on study (including any protocol-required post-treatment follow-up).

Investigators are not obligated to actively seek AEs or SAEs beyond the follow up period for subjects. However, if the investigator learns of an AE or SAE that occurs after the completion of termination visit and the event is deemed by the investigator to be related to the study treatment (following the guidelines in Section 8.1.5), he/she should promptly document and report the event to Inovio Pharmaceuticals.

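### Dosed subjects who leave early stay in the SAE denominator, but new non-fatal SAEs after they leave are not actively sought

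*Combined protocol and SAP*

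**What the plan says.** Section 3 plans safety follow-up for 6 months from the last dose, and section 6.3.4.2 collects adverse events from consent to the End of Study visit.

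Section 4.4.1 treats anyone who does not complete the protocol as having discontinued the study early. Its reasons for withdrawal include intercurrent illness (item 1), unacceptable toxicity (item 2), "Treatment delay greater than four weeks for any toxicity" (item 5), poor compliance (item 6) and major protocol violations (item 7), among them "failure to complete full evaluations as required by protocol". Closing evaluations are done at discontinuation where possible. A separate paragraph covers a subject who stops Study Treatments before the 6 months are complete and asks for the end-of-treatment and/or end-of-study assessments.

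Section 4.4.2, on withdrawn subjects, makes two provisions: "Subjects taken off study due to treatment related toxicity will be followed until resolution or stabilization", and survival status for everyone. Section 8.1.8 says that all AEs and SAEs "must be reported for subjects on study (including any protocol-required post-treatment follow-up"), with no duty to search actively beyond the follow-up period. Events learned of after the termination visit are reported if judged related.

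On the analysis side, section 7.3 says "Any subject who receives at least one dose of treatment will be included in the safety analyses", and section 7.2 says "The incidence of SAEs and the incidence of injection site reactions will be estimated along with exact Clopper Pearson 95% confidence intervals".

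**The concern.** Safety is the primary endpoint, and the SAE incidence is not restricted to related events. A subject who leaves after one or two doses for non-compliance or a protocol violation can usually still be asked about SAEs. As written, the plan does not clearly require that. A new, non-fatal SAE after exit can go unrecorded while the subject remains in the denominator and counts as SAE-free for time that nobody observed. Section 7.2 makes no allowance for unequal observation. Unobserved time can lower the SAE count but cannot raise it, so any bias is downward. In a study of 20 to 25 subjects, a few such leavers matter to the one precision statement that the plan makes.

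**Working it through.** **The plan's own figure.** Section 7.1 states that 0 SAEs in 20 subjects excludes a true incidence of 17% or more with 95% confidence. The two-sided exact (Clopper-Pearson) upper limit for 0 events in n is 1 − 0.025^(1/n). With n = 20 it is 1 − 0.025^(1/20) = 0.1684, or 16.8%. The figure reproduces, provided that all 20 are observed for the whole window.

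**Assumptions for early leavers.** The documents give no dropout rate, so the number of leavers k is assumed to be 2 or 4 of 20. Two treatments of a leaver's time bracket the effect:

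- *Half credit.* Each leaver is observed for half the window, with constant hazard (assumed). The effective number is T = 20 − k + k/2 and the limit is 1 − 0.025^(1/T).
- *No credit.* Leavers contribute nothing, so n = 20 − k. This is the worst case, because events up to the closing visit are in fact recorded.

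| Leavers of 20 (assumed) | Limit the analysis reports | Half credit | No credit |
|---|---|---|---|
| 0 | 16.8% | 16.8% | 16.8% |
| 2 | 16.8% | T = 19: 17.6% | n = 18: 18.5% |
| 4 | 16.8% | T = 18: 18.5% | n = 16: 20.6% |

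**Bias in the estimate.** Take a true full-window SAE risk of 17% (assumed) and half-window observation for leavers. A leaver's observable risk is 1 − 0.83^0.5 = 0.0890. The expected crude incidence is (18 × 0.17 + 2 × 0.0890)/20 = 16.2% with 2 leavers and (16 × 0.17 + 4 × 0.0890)/20 = 15.4% with 4. The chance of seeing no SAE at all rises from 0.83^20 = 2.4% to 0.83^19 = 2.9% and 0.83^18 = 3.5%.

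**At the upper enrolment.** With 25 fully observed subjects the limit is 1 − 0.025^(1/25) = 13.7%. With 4 of 25 given no credit, n = 21 and the limit is 16.1%. With 5, n = 20 and it is 16.8%.

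**The case against.** The strongest reply is that the plan captures more than section 4.4.2 alone suggests. Survival is tracked for everyone. The clarification under section 8.1.3 follows ongoing SAEs to resolution, and item 2 of section 4.4.1 follows unacceptable toxicity to resolution or stabilization. Neither carries a causality condition. A reader might infer from section 4.4.2 that all safety follow-up after exit turns on the causality call, and those two provisions show that it does not. They cover events already present at exit, however, not new ones.

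A reader might also infer that every early leaver gets exactly one closing visit. The paragraph on stopping Study Treatments can be read as keeping the end-of-study visit, which is defined as the last long-term follow-up visit, or as bringing it forward. The text does not settle this. Section 6.3.4.7 shows that the protocol can make the separation: after a positive pregnancy test dosing stops but follow-up continues. Section 8.1.8 likewise lifts the duty of active search beyond the follow-up period and does not name early withdrawal. The ambiguity is real, and it is what needs repair.

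It is tempting to add that item 7c, "use of concomitant therapies", contradicts section 6.6.1, where "Subjects will be offered an analgesic (e.g. ibuprofen, ketorolac) after vaccination/EP", so that accepting the offer would be a major violation. That reading does not hold. Item 7c sits under protocol violations, section 8.3.5 describes a violation as a departure from the approved protocol, and taking what the protocol directs sites to offer is not a departure. The item is at most loosely worded, and it has no bearing on the SAE estimate.

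Finally, the effect may be small. The summary of changes reports 19 subjects already followed for more than 6 months (it does not say from when), replacement of leavers is considered, and up to 25 may be enrolled. With 25 enrolled and as many as 5 given no credit, the limit still meets the stated <17%. Injection site reactions, the other primary estimate, are assessed within 30 to 45 minutes of dosing and recorded for 3 days, so they are little affected. All of this limits the size of the problem but leaves the gap in place.

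**Conclusion.** The concern holds in a limited form. Following the plan as written can miss new non-fatal SAEs after early exit, while the crude proportion counts those subjects as if observed for the full 6 months after the last dose. The direction is downward. For 20 subjects and 0 SAEs, the 16.8% limit becomes 17.6% to 18.5% with 2 leavers and 18.5% to 20.6% with 4, running from half credit to no credit. The higher figure of each pair is a worst case, not the limit that the data would support. Leaver counts, half-window observation and constant hazard are all assumptions, and the documents do not allow the actual size to be fixed. Withdrawal of consent does end observation and is not part of the point. This is a cheap improvement to the primary estimate and does not invalidate the design.

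**What to change.** In sections 4.4.1 and 4.4.2, separate discontinuation of Study Treatment from withdrawal from the study. State that dosed subjects who stop under items 1, 2, 5, 6 or 7 remain on the scheduled AE and SAE follow-up through 6 months after the last dose received, whatever the causality call, unless consent is withdrawn. Align section 8.1.8 so that these subjects count as on study.

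In section 7.2, for all dosed subjects, including those discontinued for progression or new anti-cancer therapy, report beside the SAE incidence the number observed for the full window and the observation time. This can be done at analysis even for subjects whom the wording change comes too late to reach.

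The cost is protocol wording, two extra figures in the safety table, and at most two already scheduled visits (or contacts where a visit is refused) per early leaver. No dose or rule for stopping treatment changes.

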## 5 Study Drug

### 5.1 Description

Investigational product is defined as a pharmaceutical form of an active ingredient or placebo being tested or used as a reference in the study.

VGX-3100, the active investigational product to be used in this study, is a mixture of two separate DNA plasmids encoding E6 and E7 proteins of HPV types 16 and 18. INO-9012 is a DNA plasmid expressing the p35 and p40 human IL-12 subunits off of separate promoters within the same plasmid. VGX-3100 and INO-9012 combination is referenced as INO-3112.

INO-3112 (6 mg VGX-3100 + 1 mg INO-9012) is delivered by IM with EP for subjects in Cohort I and Cohort II. INO-3112 will be provided by Inovio Pharmaceuticals, Inc. or its designee.

**Table 5.1** Investigational Products

| Product  | Concentration | Dosage Form & Route of Administration   | Dose a (mL) |
|----------|---------------|---|------------------------|
| VGX-3100 | 6 mg/mL*      | Sterile water for injection with 1% poly-L-glutamate sodium salt via IM injection | 1.1 #       |
| INO-9012 | 10 mg/mL*     | Sterile water for injection via IM injection                                      |                        |

\*Target concentration of the DNA plasmid. The actual concentration may vary slightly in the lot used for this study.

aVGX-3100 and INO-9012 combined to deliver 1.1 mL (Cohorts I and II).

#There is no exception on dosing change in immunotherapy for any cohort

### 5.2 Packaging

VGX-3100 and INO-9012 vials will be shipped directly from the manufacturer or its designee to each individual study site or regional depot. Each vial will be labeled with a single panel label. Vials will only be handled by designated personnel (e.g. pharmacist) at each site. When a subject is eligible for enrollment, personnel will combine the appropriate investigational products as detailed in section 5.3.5 (Preparation of Investigational Product) then provide to the clinical personnel. Sample vial text for each investigational product is provided below:

|          |   |
|----------|---|
| VGX-3100 | SynCon™ VGX-3100 [6mg/mL] 1 mL/vial
Lot: VGX-3100. xxxxxx
Date of Manufacture: DD MMM YY
Final Retest Date: DD MMM YY
Store frozen at or below -15C
CAUTION: New Drug – Limited by Federal Law to Clinical Trial Use Only
Inovio Pharmaceuticals Inc [name] |
|----------|---|

|          |  |
|----------|--|
| INO-9012 | SynCon™ INO-9012 [10 mg/mL]
0.2 mL/vial Single Use Vial
Lot: INO-9012.xxxxxx
Date of Manufacture: DD MMM YY
Final Retest Date: DD MMM YY
Store frozen at or below -15°C
CAUTION: New Drug – Limited by Federal
Law to Investigational Use.
Inovio Pharmaceuticals Inc. Rev 000 |
|----------|--|

### 5.3 Receiving, Storage, Dispensing and Return

#### 5.3.1 Receipt of Drug Supplies

Inovio Pharmaceuticals, Inc. will be responsible for assuring the quality of the investigational product is adequate for the duration of the trial. Unless otherwise specified, the product will be shipped frozen on dry ice. If there is no dry ice remaining in the shipment container when the shipment is received Inovio, or its designee should be contacted immediately.

#### 5.3.2 Storage

Investigational product(s) should be stored in a secure area according to local regulations. The product should be transferred from the shipping container to the appropriate storage conditions (frozen at -15°C or below) upon arrival.

Freezer and refrigerator temperature logs must be maintained at the clinical site and temperatures must be recorded and monitored regularly.

The principal investigator and study team will ensure that a current record of investigational product disposition is maintained at the study site where investigational product is inventoried and disposed. Records or logs must comply with applicable regulations and guidelines, and should include:

- Amount received and placed in storage area;
- Amount currently in storage area;
- Label ID number or batch number and use date or expiry date;
- Dates and initials of person responsible for each investigational product inventory entry/movement;
- Amount dispensed to each subject, including unique subject identifiers;
- Amount transferred to another area/site for dispensing or storage;
- Amount returned to Sponsor;
- Amount destroyed at study site, if applicable.

#### 5.3.3 Dispensing of Study Drug

It is the responsibility of the Investigator to ensure that product is only dispensed to study participants. It must be dispensed only from official study sites by authorized personnel according to local regulations. The site will identify a dedicated investigational pharmacist to dispense IP. Their duties will include the receipt, storage, preparation and maintenance of records for the IP.

The VGX-3100 and INO-9012 vials should be removed from the freezer and thawed at room temperature to ensure complete thaw. The thawed product must be used within 4 hours of removal from freezer. All material removed from the freezer must not be re-frozen.

### 5.3.4 Precautions with Investigational Medicinal Product

A dose of the study product known or suspected to have been taken (accidentally or intentionally) exceeding the dose mandated by the protocol, and any misuse or abuse of study products or any other product taken as a concomitant medication, whether or not associated with an adverse experience, must be reported to Inovio Pharmaceuticals within 24 hours. Any clinical sequelae in association with the overdose should be reported as an AE or SAE. Details of signs or symptoms, clinical management, and outcome should be reported, if available.

### 5.3.5 Preparation of Investigational Product

Prior to administering to subjects the investigational products will be combined by authorized personnel into a single syringe using the following procedure:

- Required Materials:
- (1) or (2) vials SynCon™ VGX-3100, thawed
  - (1) vial SynCon™ INO-9012, thawed
  - (1) 2 mL sterile empty vial
  - (1) 0.5 mL or 1.0 mL syringes
  - (2) 3 mL syringes
  - (1) 21 gauge, 2” needle
  - (2) 21 gauge, 1.5” needles

**Note: The second vial of SynCon™ VGX-3100 should only be thawed if less than 1.1 mL is withdrawn from the first vial in Step (1) below:**

1. Using aseptic technique, withdraw the **entire contents** from the vial SynCon™ VGX-3100 with a 3 mL syringe and a 2” 21 gauge needle; a needle of a minimum length of 2” is recommended to be able to withdraw the entire contents of the larger vial.
2. If the volume of VGX-3100 in the syringe is **less than 1.1 mL**, perform Formulation Instruction Set A.
3. If the volume of VGX-3100 in the syringe is **exactly 1.1 mL**, perform Formulation Instruction Set B.
4. If the volume of VGX-3100 in the syringe is **1.2 mL or more**, perform Formulation Instruction Set C.

**Formulation Instruction Set A (less than 1.1 mL VGX-3100 withdrawn):**

1. Thaw a second vial of SynCon™ VGX-3100.
2. Once the vial is thawed, using the same syringe/needle from the first vial, withdraw a sufficient volume of VGX-3100 from the second vial to total **at least 1.2 mL** of VGX-3100 in the syringe.
3. Inject **1.2 mL** of VGX-3100 into an empty sterile vial; set this “mixing” vial which now contains 1.2 mL of VGX-3100 aside.

4. Using a new 0.5 or 1.0 mL syringe with a 1.5” 21 gauge needle, withdraw **0.12 mL** from the vial SynCon™ INO-9012 and add the 0.12 mL to the “mixing” vial containing 1.2 mL of VGX-3100. The final volume of this vial should now be approximately 1.32 mL of VGX-3100 and INO-9012.
5. Ensure the contents of the “mixing” vial are well mixed by gently inverting the vial several times.
6. Using a 3 mL syringe with a 1.5” 21 gauge needle, withdraw **1.1 mL** of VGX-3100 and INO-9012 from the “mixing” vial. This syringe will be used for dosing of subjects.

**Formulation Instruction Set B (exactly 1.1 mL VGX-3100 withdrawn):**

1. Inject **1.1 mL** of VGX-3100 into an empty sterile vial; set this “mixing” vial which now contains 1.1 mL of VGX-3100 aside.
2. Using a new 0.5 or 1.0 mL syringe with a 1.5” needle, withdraw **0.11 mL** from the vial SynCon™ INO-9012 and add the 0.11 mL to the “mixing” vial containing 1.1 mL of VGX-3100. The final volume of this vial should now be approximately 1.21 mL of VGX-3100 and INO-9012.
3. Ensure the contents of the “mixing” vial are well mixed by gently inverting the vial several times.
4. Using a 3 mL syringe with a 1.5” 21 gauge needle, withdraw **1.1 mL** of VGX-3100 and INO-9012 from the “mixing” vial. This syringe will be used for dosing of subjects.

**Formulation Instruction Set C (1.2 mL or more of VGX-3100 withdrawn):**

1. Inject **1.2 mL** of VGX-3100 into an empty sterile vial; set this “mixing” vial which now contains 1.2 mL of VGX-3100 aside.
2. Using a new 0.5 or 1.0 mL syringe with a 1.5” needle, withdraw **0.12 mL** from the vial SynCon™ INO-9012 and add the 0.12 mL to the “mixing” vial containing 1.2 mL of VGX-3100. The final volume of this vial should now be approximately 1.32 mL of VGX-3100 and INO-9012.
3. Ensure the contents of the “mixing” vial are well mixed by gently inverting the vial several times.
4. Using a 3 mL syringe with a 1.5” 21 gauge needle, withdraw **1.1 mL** of VGX-3100 and INO-9012 from the “mixing” vial. This syringe will be used for dosing of subjects.

Replace the 1.5” needle with 2” 21 gauge needle of the syringe for dosing of subjects. The syringe must be labeled with a four-hour expiration time from the time the vial is removed from the freezer. The label should also contain the words “administer as soon as possible”.

**5.3.6 Return or Destruction of Study Drug**

Upon completion or termination of the study, all unused and/or partially used investigational product must be returned to Inovio Pharmaceuticals, Inc., or its designee, if not authorized by Inovio Pharmaceuticals, Inc. to be destroyed at the site. All investigational products returned to Inovio Pharmaceuticals, Inc., or its designee, must be accompanied by the appropriate documentation. Returned supplies should be in the original containers. Empty containers should not be returned to Inovio Pharmaceuticals, Inc. It is the Investigator’s responsibility to arrange for

5. Tumor Evaluation: Confirmation of diagnosis by histology and confirmation of p16 positivity. While biopsy tissue samples are undergoing confirmation of p16 positivity, the subject may proceed to other screening procedures and tests. However, the subject will be dosed only upon confirmation of p16 positivity or other pathological evidence of oncogenic HPV infection. Confirmation of diagnosis of surgically resectable HNSCCa.
6. 12-lead ECG.
7. Clinical laboratory testing including, but not limited to: CBC with differential and platelet count, PT, INR/PTT, total serum bilirubin, alkaline phosphatase, AST (SGOT), ALT (SGPT), serum creatinine, serum electrolytes, serum calcium, serum albumin and CPK.

Note: If clinical lab testing is performed within 28 days prior to study Day 0 as standard of care, the results can be used for screening and eligibility assessment.

8. Serology (HIV Ab, HCV Ab, HBsAg).
9. Serum beta HCG (for women of child bearing potential).
10. Adverse Events
11. Whole blood and serum for baseline immunologic assays.
12. Paraffin-embedded tumor tissue or unstained slides for ISH and IHC.

On the rare occasions where a subject is re-screened, the clinical labs and 12-lead ECG must be repeated unless they occur within 4 weeks of the subject's first dose. All other screening procedures do not need to be repeated.

